### **7.3 Study as a Whole**

Both the Sponsor and the Investigator reserve the right to terminate the study at the Investigator's site at any time. Should this be necessary, the Sponsor or a specified designee will inform the appropriate regulatory authorities of the termination of the study and the reasons for its termination, and the Investigator will inform the IRB of the same. In terminating the study, the Sponsor and the Investigator will assure that adequate consideration is given to the protection of the patients' interests.

Possible reasons for termination are:

- Safety reasons –the incidence of AEs in this or any other study using the same investigational product(s) indicates a potential health risk for the patients
  - New scientific knowledge becomes known that makes the objectives of the study no longer feasible/valid
  - Unsatisfactory enrollment of patients
-

## **8 DESCRIPTION OF STUDY PROCEDURES**

Patients will be solicited from medical office, clinics, or hospitals where they seek care for COVID-19 symptoms and where COVID-19 test positivity is documented. All recruitment materials will be reviewed by the Institutional Review Board overseeing the study. Patients need not have a personal doctor to participate in the study. Patients themselves must provide written informed consent before the performance of any study-related procedures, and surrogate consent by family members, designated legal representatives, or caregivers will not be permitted. In the event that the patient progresses to hospitalization or is unable to complete the eDiary or telephone calls, designated legal representatives, family members or caregivers will be contacted, as provided by informed consent, for this information.

### **8.1 Screening Assessments**

#### **8.1.1 *Demographics***

Demographic data (age, sex, race, ethnicity) will be recorded during Screening. The name and contact information for the patient's family member(s) or caregiver(s) will also be obtained in the event that the eDiary ([Section 8.2.2](#)) is not completed patient does not respond to telephone calls ([Section 8.2.3](#)). The contact information for the patient's personal doctor (s) will also be obtained.

#### **8.1.2 *Medical History***

A complete medical history, including diabetes, hypertension, and respiratory history, is to be documented during Screening. Smoking history of use of any inhalation products (eg, nicotine-containing products including e-cigarettes or e-vaporizers) is to be documented.

The patient's COVID-19 symptom history, including fever (temperature >100.4°F [38.0°C]), fatigue, chills, headache, cough (with or without sputum production), myalgia, sore throat, shortness of breath, nasal congestion, diarrhea, and nausea or vomiting is to be documented, including date of onset of symptoms, and any laboratory or radiological test results obtained.

The date of initial SARS-CoV-2 positivity also is to be documented.

#### **8.1.3 *Pregnancy Testing (Females of Childbearing Potential Only)***

A urine pregnancy test is to be performed for female patients of childbearing potential at Screening. Results must be available and confirmed to be negative before study drug administration.

#### **8.1.4 *Concomitant Medications***

Concomitant medications will be documented, per [Section 6.7](#).

---

## **8.2 Efficacy Assessments**

### **8.2.1 *Pulse Oximetry, Pulse Rate, and Temperature***

After signing informed consent, patients will be provided with a fingertip pulse oximetry device that connects to a mobile device connecting to a tablet that will be supplied to the patient to measure resting SpO2 and resting pulse rate. Patients will be trained on the use of the device and tablet. This device will be used to determine study eligibility at Screening, and if the patient is eligible, he/she will return home with the device for remote monitoring of resting SpO2 and resting pulse rate for the duration of the study.

#### *8.2.1.1 Screening*

Resting SpO2 and resting pulse rate will be measured twice at Screening, with each measurement being of 2 minutes duration. For the first measurement, the patient will be sitting and breathing room air for at least 5 minutes before the measurement is made. A 3- to 5-minute interval will transpire before the second measurement is commenced. The patient should continue to sit and breath room air through the time that the second measurement is completed. To ensure stabilization of resting SpO2, only the average of resting SpO2 and resting pulse rate in the second minute of each measurement will be used to determine study eligibility. To be eligible for the study, patients will be required to have an average resting SpO2  $\geq$  96.0% and average resting pulse rate  $<$  125 beats per minute on both measurements. Baseline for resting SpO2 and resting pulse rate will be defined as the mean of the two measurements. Oral temperature will also be recorded.

#### *8.2.1.2 Home Monitoring*

Resting SpO2 and resting pulse rate will be measured remotely twice daily at 09:00 hours and 16:00 hours for 14 days, with each measurement being of 2 minutes duration and with a 1-hour window around each time point. They will also record resting SpO2 and resting pulse rate at any time they experience worsening symptoms. The patient will be sitting at rest and breathing room air for at least 5 minutes before these measurements are made and should continue to sit and breath room air through the time that the measurement is completed. To ensure stabilization of resting SpO2 and resting pulse measurements, only the averages of these parameters in the second minute of measurement will be analyzed.

Similarly, patients will be provided with a digital thermometer to measure oral temperature at 09:00 hours and 16:00 hours twice daily, with a 1-hour window around each time point, and at any time they experience worsening symptoms through Day 14, with results recorded in the eDiary.

Resting SpO2 and resting pulse rate measurements will automatically be captured in the mobile device, while oral temperature will be captured in the eDiary ([Section 8.2.2](#)).

The Screening visit is defined as Day 1. If the visit occurs in the morning, the patient will be responsible for recording the 16:00-hour measurements at home later that day; if the

---

visit occurs after 16:00 hours, measurements will commence at home the following morning.

### **8.2.2**      *eDiary*

The eDiary will be completed by patient each day through Day 14. The following symptoms will be collected:

- Fatigue
- Chills
- Headache
- Cough (with or without sputum production)
- Myalgia
- Sore throat
- Shortness of breath
- Nasal congestion
- Diarrhea
- Nausea or vomiting

For each of these symptoms, the patient will be asked to grade them by the following scale:

- Not at all
- A little bit
- Somewhat
- Quite a bit
- Very much

The patient will also record all temperatures in the eDiary.

In the event that the patient progresses to hospitalization or is unable to complete the eDiary, family members, designated legal representatives or caregivers will be contacted, as provided by informed consent, to determine the status of the patient.

### **8.2.3**      *Telephone calls*

The patient will be called each day, Day 2 through Day 14. The telephone script is provided in [Appendix A](#).

After the completion of Day 14, the patient will be called weekly through Day 28. The telephone script is provided in [Appendix B](#).

---

Based on the findings of telephone calls, an Unscheduled Visit with the Investigator or personal doctor may be scheduled ([Section 8.4](#)).

In the event that the patient progresses to hospitalization or is unable to complete the telephone calls, family members or caregivers will be contacted, as provided by informed consent, to determine the status of the patient.

#### **8.2.4      *Criteria for the Assessment of Severity of Illness in Patients with COVID-19***

The criteria in [Appendix C](#) will be used to assess changes in the severity of COVID-19 in patients at different timepoints over the course of the trial. The final determination will be made on Day 28 in patients who are not hospitalized and Day 42 in patients who are hospitalized.

#### **8.2.5      *Additional Data Collection in Hospitalized Patients***

Additional data to be collected for patients hospitalized due to COVID-19 through Day 42 to include the following:

- Date and time of hospital admission and discharge
- If transferred to ICU, date and time of ICU admission and discharge
- Requirement for oxygen (yes/no), and if yes, method of oxygenation (mask/nasal prongs, non-invasive ventilation, or high-flow oxygen; intubation and mechanical ventilation
  - If required ventilation, start date and time of ventilation, method of ventilation including whether intubated (yes/no)
- Change in ambulatory status
- Death

It is anticipated that most of this information will be obtained from the medical record. When necessary, a family member, designated legal representative or caregiver, as permitted by informed consent, will be contacted if the patient has expired or is too ill or otherwise unable to provide this information.

The rate (liters/min) of oxygen administered is to be captured as a concomitant medication. If, in the Investigator's opinion, a patient required a higher level of oxygenation, but did not receive due to resource availability, this should be documented.

---

Furthermore, if, in the Investigator's opinion, the patient required a higher level of care (ie, admittance to the ICU) but did not receive due to resource availability, this should be documented.

### **8.2.6 Vital Status**

Vital status is to be documented at each study contact. If the patient died due to a reason other than COVID-19, the primary cause of death is to be recorded and reported as an SAE. Death due to worsening fever, cough, shortness of breath, resting SpO2, or resting pulse rate or COVID-19 symptoms that are reported at Screening ([Section 8.1.2](#)) is not considered to be an SAE in the context of this study although cause of death will be reviewed by the DMC in real time.

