### **9.2      *Reporting Responsibilities and Periods***

It is the responsibility of the Investigator to perform periodic assessment for AEs. AEs spontaneously reported by the patient or reported in response to an open question from the study personnel (eg, 'Have you had any health problems since the previous visit/you were last asked?') or revealed by observation will be recorded.

AEs and concomitant medications will be recorded from the start of study drug administration on Day 1 through 14 or until the time of hospitalization. The AE term, date of AE onset, date of AE resolution (if applicable), severity, causality, action taken for the AE, outcome and whether or not the AE was serious will be recorded.

---

AEs must be monitored until they are resolved, stabilized or transferred to the patient's main healthcare provider for follow up, are clearly determined to be due to a patient's stable or chronic condition or intercurrent illness(es), the patient is hospitalized, or follow-up is no longer possible. Data describing AEs will be recorded in the patient's medical record and as appropriate, an SAE report form. SAEs will be reported to the Sponsor as described in [Section 9.6](#).

Any SAE that the Investigator considers to be related to study drug and occurs at any time after completion of the study must be reported to the Sponsor or designee. If at the time the Investigator initially reports an SAE, the event has not resolved, the Investigator must provide a follow-up report as soon as it resolves (or upon receipt of significant information if the event is still ongoing).

Note that for the purposes of this study, hospitalization due to worsening fever, cough or shortness of breath, resting SpO2 or resting pulse rate or symptoms of COVID-19 that are reported prior to treatment ([Section 8.1.2](#)) will not be considered an SAE.

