### **9.6.3 Special Reporting Situations**

#### ***Hospitalization or Death***

Hospitalization and death are outcomes of an event. The event that resulted in hospitalization or death should be recorded and reported on the SAE form and the AE eCRF page.

As noted in [Section 9.2](#) and [Section 8.2.6](#), hospitalizations and deaths related to worsening fever, cough, shortness of breath, resting SpO2 or resting pulse rate or symptoms of COVID-19 at Screening ([Section 8.1.2](#)) will not be considered SAE, although narratives of the hospitalizations and causes of death will be reported to and reviewed by the DMC in real time.

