7.2 Reporting Responsibilities and Periods

It is the responsibility of the Investigator to perform periodic assessment for AEs. AEs spontaneously reported by the patient or reported in response to an open question from the study personnel (eg, ‘Have you had any health problems since the previous visit/you were last asked?’) or revealed by observation will be recorded.

AEs and concomitant medications will be recorded from the start of study drug administration on Day 1 through 14 or until the time of hospitalization. The AE term, date of AE onset, date of AE resolution (if applicable), severity, causality, action taken for the AE, outcome and whether or not the AE was serious will be recorded.

AEs must be monitored until they are resolved or, stabilized or transferred to the patient’s main healthcare provider for follow up., are clearly determined to be due to a patient’s stable or chronic condition or intercurrent illness(es), the patient is hospitalized or follow-up is no longer possible. Data describing AEs will be recorded in the patient’s medical record and as appropriate, an SAE report form. SAEs will be reported to the Sponsor as described in Protocol Section 9.6.

Any SAE that the Investigator considers to be related to study drug and occurs at any time after completion of the study must be reported to the Sponsor or designee. If at the time the Investigator initially reports an SAE, the event has not resolved, the Investigator must provide a follow-up report as soon as it resolves (or upon receipt of significant information if the event is still ongoing).

Note that for the purposes of this study, hospitalization due to worsening fever, cough or shortness of breath, resting SpO₂ or resting pulse rate or symptoms of COVID-19 that are reported at Baseline will not be considered an SAE.

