7.6.2 Special Reporting Situations

Hospitalization or Death

Hospitalization and death are outcomes of an event. The event that resulted in hospitalization or death should be recorded and reported on the SAE form and the AE eCRF page.

As noted in Protocol Section 9.2 and Section 8.2.6, hospitalizations and deaths related to worsening fever, cough, shortness of breath, resting SpO₂ or resting pulse rate or symptoms of COVID-19 at Screening will not be considered SAE, although narratives of the hospitalizations and causes of death will be reported to and reviewed by the DMC in real time.

Surgical or Diagnostic Procedures

The illness leading to a surgical or diagnostic procedure is to be recorded as an AE/SAE, not the procedure itself. The procedure is to be captured in the case narrative as part of the action taken in response to the illness.

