9.5 Analysis Populations

Consented Population: All patients who signed the informed consent.

Randomized Population: All patients who were randomized to receive any study medication.

Safety Analysis Set: All patients who receive any study drug. Patients will be analyzed according to the treatment that they receive.

Modified Intent-to-Treat (mITT) Analysis Set: All randomized patients who receive any amount of study drug, have a Baseline and at least one post-Baseline resting SpO₂ measurement. Patients will be analyzed according to the treatment that they receive. Patients will be analyzed according to the treatment that they receive. This analysis set will be used for primary and secondary analyses.

Per Protocol (PP) Set: All randomized patients who receive any amount of study drug according to the correct treatment assignment and who have 80% of twice daily results from resting SpO₂ measurements through Day 14 or hospitalization.

All important protocol deviations documented during study will be collected and finally assessed as major or minor protocol deviation after data base lock and prior to unblinding.

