9.10.2 COVID-19 Symptoms

Each patient will record the following COVID-19 symptoms daily in the eDiary with the study-supplied devices (ie, tabloid, digital thermometer) through Day 14. For patients who are unable to complete the eDiary, the records of symptoms will be collected over the telephone.

- fatigue, chills, headache, cough (with or without sputum production), myalgia, sore throat, shortness of breath, nasal congestion, diarrhea, nausea or vomiting, and oral temperature.

The patient will be asked to grade the symptoms in scale of “not at all”, “a little bit”, “somewhat”, “quite a bit”, and “very much”.

A cumulative summary of the number and percentage of patients experiencing at least one symptom (as local, systemic, and overall) through Day 14 will be tabulated by maximum severity and treatment group. Differences between each NasoVAX cohort and pooled placebo for cumulative events (local, systemic, and overall) will be tested using Kruskal-Wallis tests. The number and percentage of subjects experiencing at least one grade of “quite a bit” and “very much” symptom through Day 14 days for each symptom type, as well as 95% Clopper Pearson exact CIs, will be presented by treatment group.

A summary of the number and percentage of subjects experiencing at least one event through Day 14 will also be tabulated by event type, maximum severity, and treatment group. In addition, a descriptive summary of the duration of events (regardless of severity) will be tabulated by event and dose group.

Generally, symptoms recorded in the eDiary and (unsolicited) AEs recorded in the AE log will be summarized separately. A change in symptoms from baseline will not be recorded as an (unsolicited) AE unless it meets the criteria of an SAE. Any event found in the AE log that is also captured in the eDiary will not be counted as an AE to avoid duplication.

9.10.3 *Safety Laboratory Tests and Vital Signs*

Clinical laboratory results will be listed for urinalysis. Presentations will use SI Units.

Observed and change from baseline of continuous clinical laboratory values will be summarized descriptively by each treatment group and visit. Summary statistics for continuous parameters will be presented by treatment group as follows: pre-treatment, post-treatment, and change from pre-treatment to post-treatment assessment.

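### The SAP contradicts itself on whether serious COVID-19 worsening counts as an AE/SAE, and under one of its two rules an early COVID-19 death can be absent from both the SAE tables and the mITT mortality analysis

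*Protocol*

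**What the plan says.** **The exclusion.** Protocol 8.2.6 says that a death from worsening of the listed COVID-19 signs, or of symptoms reported at Screening, "is not considered to be an SAE in the context of this study". Protocol 9.2 says that hospitalization on the same grounds "will not be considered an SAE". Protocol 9.6.3 covers both: they "will not be considered SAE, although narratives of the hospitalizations and causes of death will be reported to and reviewed by the DMC". The SAP carries this over. Section 6.2.6 repeats the rule for death, and 7.2 repeats it for hospitalization ("reported at Baseline will not be considered an SAE"). Section 7.6.2 repeats it for both ("will not be considered SAE, although narratives of the hospitalizations"). SAP 7.1.1 adds that such worsening is captured in aggregate and is not reported as an AE.

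**The symptom rule.** SAP 9.10.2 says that a change in symptoms from baseline "will not be recorded as an (unsolicited) AE unless it meets the criteria of an SAE". Its next sentence removes from the AE count any AE-log event that the eDiary also captured, and names no exception for serious events.

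**The analysis set.** Under SAP 9.5, mITT patients must be randomized, receive study drug and "have a Baseline and at least one post-Baseline resting" SpO2 measurement. The same section assigns this set to the primary and secondary analyses. Mortality to Day 42 is a secondary efficacy endpoint (SAP 3.2). Home readings stop at hospitalization (protocol 4.1).

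**The concern.** The first problem is that two programmers could follow the SAP faithfully and produce different AE and SAE tables. The general SAE definition in SAP 7.1.3 includes death and inpatient hospitalization. Read against that definition, 9.10.2 brings in events that 7.1.1, 7.2 and 7.6.2 keep out. SAP 9.13 puts the SAP above the protocol, but that does not help when one SAP section disagrees with another.

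The second problem arises if the exclusion is the rule applied. The efficacy analyses are then the main place where serious COVID-19 outcomes are compared between arms, and those analyses require a post-Baseline SpO2 reading. A dosed patient who is admitted or dies before giving one is in neither the SAE tables nor the mITT set.

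The protocol gives signals of adverse or paradoxical effects as what the DMC must look for before relaxing the risk-factor exclusions (protocol 4.3, 5.3 and 9.7). Rapid deterioration after dosing is one form that such an effect could take, so the reported tables should not be able to lose it.

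**Working it through.** The plan states no event rate, effect size or power, so there is no figure to reproduce. The check sets the rules side by side, then shows how much a few early events could matter under stated assumptions.

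**Step 1. Where each event is counted, by rule**

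| Event | Exclusion applied (SAP 6.2.6, 7.1.1, 7.2, 7.6.2) | 9.10.2 read against the general SAE definition |
|---|---|---|
| COVID-19 admission after a first SpO2 reading | Not an SAE; counts in the primary endpoint | AE/SAE unless de-duplicated; counts in the primary endpoint |
| COVID-19 admission before any post-Baseline reading | Not an SAE; outside mITT; visible through length of stay | AE/SAE unless de-duplicated; outside mITT |
| COVID-19 death after a first reading | Not an SAE; in mITT mortality | AE/SAE unless de-duplicated; in mITT mortality |
| COVID-19 death before any post-Baseline reading | Not an SAE; outside mITT mortality | AE/SAE unless de-duplicated; outside mITT mortality |

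In the overall TEAE summary of SAP 9.10.1, the item for deaths is restricted to SAEs, so a death that is not an SAE is not in it. Death is not among the safety endpoints (SAP 3.3) or the listed reasons for discontinuation (SAP 5.1.1). An early death at home has no length of stay either.

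**Step 2. The unobserved window.** After a visit ending at 16:00 with no reading at the center, the first scheduled home reading is due at 09:00 the next day, plus or minus 1 hour. That is 16 to 18 hours later, and longer if readings are missed.

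**Step 3. Chance of at least one such patient.** The arms are 10 + 14 + 24 = 48 each, 96 in all. Let q be the assumed probability that a patient is admitted or dies of COVID-19 before any post-Baseline reading. Then P(at least one) = 1 - (1 - q)^96, and the expected number is 96q.

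| q (assumed) | Expected cases | P(at least one) |
|---|---|---|
| 0.25% | 0.24 | 21% |
| 0.5% | 0.48 | 38% |
| 1% | 0.96 | 62% |
| 2% | 1.92 | 86% |

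**Step 4. Effect of one lost event.** A patient outside mITT leaves both numerator and denominator. The counts below are invented, and the loss is placed in the NasoVAX arm. An unstratified one-sided Fisher exact test stands in for the Cochran-Mantel-Haenszel test; the plan's level is 0.025 one-sided.

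| All dosed, NasoVAX vs placebo | p | One NasoVAX event lost | p |
|---|---|---|---|
| 5/48 vs 5/48 | 0.630 | 4/47 vs 5/48 | 0.514 |
| 5/48 vs 10/48 | 0.130 | 4/47 vs 10/48 | 0.079 |
| 3/48 vs 10/48 | 0.035 | 2/47 vs 10/48 | 0.015 |

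Only the last row crosses 0.025. For mortality, one early death changes an arm from 1/48 (2.1%) to 0/47.

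**Step 5. Size of the relabelling.** At an assumed hospitalization rate of 10% (range 5-20%), 0.10 x 96 = 9.6 patients (4.8 to 19.2) could change SAE status with the section followed. This is an upper bound, because it treats every admission as due to the excluded worsening. It measures labelling, not lost events.

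**The case against.** **The rules can be read together.** The exclusion is a study-specific qualification of the general SAE definition, and the SAE criteria in 9.10.2 may mean the criteria as so qualified. The exception would still cover life-threatening events, incapacity, important medical events and symptoms that were absent at Screening. This reading is reasonable, but 9.10.2 does not state it, and 7.1.1 has no matching exception. The de-duplication sentence stays unclear under either reading.

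**The mITT gap is narrow.** This stands. Any post-Baseline reading qualifies, not only one at home. The Day 1 afternoon reading may be taken at the center (protocol Table 1, footnote c), and patients stay at least 2 hours after dosing. They are also told to measure whenever symptoms worsen. Entry requires SpO2 of at least 96.0%, and exclusion criterion 3 removes patients expected to be hospitalized within 24-48 hours. Few patients should fall in the gap, but nothing closes it.

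**The events are visible elsewhere.** This stands in part. Hospital and ICU length of stay is a summarized safety endpoint (SAP 3.3 and 9.10). The DMC receives narratives and can see unblinded data. The hospitalization stopping thresholds are first exceeded at 2 of 10, 3 of 14 and 7 of 24 per arm, whatever the SAE or mITT status. These arrangements protect patients during the trial. They do not put incidence by arm in all dosed patients into the results.

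**A table may already be planned.** SAP 9.1 says that summaries are given for each analysis set, which could include the Safety Analysis Set, but SAP 9.9 limits efficacy analyses to mITT and PP. The contents of SAP Section 11 are not in the text available, so I say only that the SAP's methods text does not call for such a table.

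**Conclusion.** The point holds in a limited form and should be fixed before database lock. The SAP has no single rule for serious COVID-19 worsening. Under the exclusion, a COVID-19 death before any post-Baseline SpO2 reading can be missing from both the SAE tables and the mITT mortality analysis. An admission in that window can be missing from the primary endpoint and visible only through length of stay. With an assumed 0.25-2% of patients affected, the chance of at least one case among 96 is 21-86%. Every rate and event count used here is an assumption.

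Four stronger readings are tempting, and the documents do not support them:

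- **That the protocol excludes these events and the SAP counts them.** The SAP repeats the exclusion in several places; the conflict is within it.
- **That the most serious outcomes are generally missing from safety and efficacy results.** Admissions after a first reading count in the primary endpoint, later deaths are in the mITT mortality analysis, and deaths from other causes remain SAEs. The double omission requires both the exclusion rule and an event before any reading.
- **That about 10 of 96 patients' events would be lost.** That figure concerns SAE labelling only.
- **That the trial cannot detect paradoxical worsening.** DMC review and the stopping rules operate independently of both definitions.

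**What to change.** 1. Reconcile SAP 9.10.2 with 7.1.1, 7.2 and 7.6.2 so that one counting rule applies, and state whether de-duplication against the eDiary applies to serious events. Cost: one or two sentences.
2. Add to SAP 9.10 a table of all hospitalizations, mechanical ventilations and deaths through Day 42, from any cause, by arm and cohort in the Safety Analysis Set, regardless of SAE status. Most of the data are already collected: protocol 8.2.5 covers COVID-19 admissions, ventilation and death, and 8.2.6 records vital status at each contact. A footnote should say that patients not in hospital at Day 28 have no further scheduled contact unless readmitted.
3. That table does not repair the mITT gap. Count hospitalization or death without a post-Baseline SpO2 reading as an event in the primary analysis, and such a death as an event in the mortality analysis, at least as a sensitivity analysis in all randomized and dosed patients. State explicitly that death counts, because the primary endpoint names only the SpO2 fall and hospitalization. Protocol 10.4 keeps the primary analysis fixed but allows further pre-specified analyses, so a sensitivity analysis fits without changing it.

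The downside is some overlap with the efficacy tables.
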